4.2 Analysis Treatment Groups for Various Analyses

Table 1.Analysis Population and Analysis Treatment Groups for Various
Analyses

		R	esected	Non- Resected (All High Dose)
Analysis	Analysis Set	Analysis Treatment Groups	Treat Group Category	Analysis Treatment Groups
Disposition	ITT	As randomized	High Dose, Low Dose, Overall	As enrolled
Baseline Characteristics, Medical History, Prior and Concomitant Medications	FAS	ATG-Day 1	High Dose, Low Dose, Overall	ATG- Day 1
Drug Exposure	Safety	ATG-All Dispensing	High Dose, Low Dose, All Low Dose, Any High Dose, Overall	ATG- Day 1

Table 1.SA Analysis Treatment Groups for Various Analyses P Version
Summary History (Continued)

			R	esected	Non- Resected (All High Dose)		
Analysis		Analysis Set	Analysis Treatment Groups	Treat Group Category	Analysis Treatment Groups		
Drug Con	npliance (wee	k 1)	Safety	ATG-Day 1	High Dose, Low Dose, Overall	ATG- Day 1	
	Primary	stool fat (Week 1 within group)	EAS-SF, EAS-SF- SUPP	ATG-Day 1	High Dose, Low Dose	ATG- Day 1	
Efficacy	Secondary	stool fat (Week 1 between group)	EAS-SF, EAS-SF- SUPP	ATG-Day 1	High Dose, Low Dose	NA	
		Stool Frequency/Stool Consistency/EPI Symptom Week 1	FAS	ATG-Day 1	High Dose, Low Dose	ATG- Day 1	
	Efficacy		Stool Frequency/Stool Consistency by visit	FAS	ATG- Dynamic	High Dose, Low Dose, Overall	ATG- Day 1
	Additional	PRO by visit (EPI/PAN 26/C30)	FAS	ATG- Dynamic	High Dose, Low Dose, Overall	ATG- Day 1	
		BMI/Weight by visit	FAS	ATG-All Dispensing	High Dose, Low Dose, All Low Dose, Any High Dose, Overall	ATG- Day 1	

Table 1.SA Analysis Treatment Groups for Various Analyses P Version
Summary History (Continued)

				R	esected	Non- Resected (All High Dose)
Analysis			Analysis Set	Analysis Treatment Groups	Treat Group Category	Analysis Treatment Groups
Efficacy Additional	Albumin and pre-albumin by visit	FAS	ATG-All Dispensing	High Dose, Low Dose, All Low Dose, Any High Dose, Overall	ATG- Day 1	
	Chemotherapy tolerability by visit	FAS	ATG-All Dispensing	High Dose, Low Dose, All Low Dose, Any High Dose, Overall	ATG- Day 1	
		AE/SAE in Week 1	Safety	ATG-Day 1	High Dose, Low Dose, Overall	ATG- Day 1
Safety		AE/SAE analyses (entire treatment period)	Safety	ATG- Dynamic	High Dose, Low Dose, Overall	NA
		All other AE/SAE analysis	Safety	ATG-All Dispensing	High Dose, Low Dose, All Low Dose, Any High Dose	ATG- Day 1
		Lab / Vital Signs	Safety	ATG-All Dispensing	High Dose, Low Dose, All Low Dose, Any High Dose	ATG- Day 1

5.0 Subject Disposition

The total number of subjects who were screened, randomized or enrolled, and treated will be summarized.

A summary of subject accountability will be provided where the number of subjects in each of the following categories will be summarized for high or low dose cohort at

randomization in the resected regimen and for subjects enrolled in the non-resected regimen:

- Subjects randomized or enrolled in the study;
- Subjects who took at least one dose of study drug;
- Subjects who completed protocol-specified treatment;
- Subjects who completed the study;
- Subjects who prematurely discontinued study drug (all reasons and primary reason);
- Subjects who prematurely discontinued study (all reasons and primary reason).

6.0 Study Drug Duration and Compliance

The overall treatment duration (irrespective of whether the subjects are receiving high dose or low dose of the study drug) will be summarized. Duration of treatment is defined for each subject as (last dose date – first dose date + 1). Duration of treatment will be summarized using the number of subjects treated, mean, standard deviation, median, minimum and maximum. In addition, the number and percentage of subjects in each treatment duration interval (< 1 Week, 1 to < 5 weeks, 5 to < 9 weeks, 9 to < 13 weeks, ≥ 13 weeks) will be summarized.

The number of capsules taken per day for the first week of treatment will be summarized for all subjects in the Safety Analysis Set. The number of meals and snacks per day reported in the dosing diary for the first week of treatment will also be tabulated.

7.0 Demographics, Baseline Characteristics, Medical History, and Prior/Concomitant Medications

Demographics, baseline or disease characteristics, medical history, and prior and concomitant medications will be summarized for the FAS population. Categorical variables will be summarized with the number and percentage of subjects; percentages will be calculated based on the number of non-missing observations. Continuous

variables will be summarized with descriptive statistics (number of non-missing observations, mean and standard deviation, median, minimum and maximum).

7.1 Demographics and Baseline and Disease Characteristics

Continuous demographic variables include baseline age, weight, height, body mass index (BMI), hip and waist circumference, and Fecal elastase-1 (FE-1). Categorical demographic variables include sex, ethnicity, race, weight (< 60 or \ge 60 kg), BMI (< 25 or \ge 25 kg/m²), tobacco user (current, former, never, unknown), alcohol user (current, former, never, unknown) and ECOG performance status.

Cancer history data will also be summarized categorically according to their histologic type, overall staging at the initial diagnosis, overall staging at study entry, anatomical location of the cancer involvement in the pancreas (head, neck, body, tail or multiple), the presence of metastatic disease at study entry (Yes or No), completion of neo-adjuvant chemotherapy or neo-adjuvant radiotherapy (Yes or No), history of resection of their primary pancreatic cancer (Yes/No).

Pancreatic Cancer resection history will also be summarized according to what procedure they went through (pancreaticoduodenectomy, polyrus preserving whipple, distal pancreatectomy, total pancreatectomy, or other).

7.2 Medical History

Medical history data will be coded using the Medical Dictionary for Regulatory Activities (MedDRA). The actual version of the MedDRA coding dictionary will be noted in the statistical tables and clinical study report. The number and percentage of subjects in each medical history category (by MedDRA system organ class and preferred term) will be summarized overall by high or low dose cohort as the study drug is dispensed to the subjects at randomization (Day 1) in the resected population and for subjects enrolled in the non-resected populations. The system organ class (SOC) will be presented in alphabetical order, and the preferred terms will be presented in alphabetical order within

each SOC. Subjects reporting more than one condition/diagnosis will be counted only once in each row (SOC or preferred term).

7.3 Prior and Concomitant Medications

Prior and concomitant medications will be summarized by generic name. The number and percentage of medications will be summarized per subject for both prior and concomitant medications.

A prior medication and procedure are defined as any medication and procedure performed prior to the date of the first dose of study drug. This includes medications and procedures with a start date before the first study drug administration date. In cases where incomplete or missing medication and procedure dates are collected, a conservative approach will be taken and it will be counted as a prior medication and procedure. Prior radiation therapies will be summarized according to the relative location category (primary, regional, distant, unknown and multiple).

A concomitant medication is defined as any medication that started prior to the date of the first dose of study drug and continued to be taken after the first dose of study drug or any medication that started on or after the date of the first dose of study drug, but not after the date of the last dose of study drug.

In the situation where an incomplete or missing medication date is collected, a conservative approach will be taken and it will be counted as a concomitant medication unless there is evidence that the medication was not taken before the study drug treatment (e.g., an end date before study drug start date).

A concomitant procedure is defined as any procedure that started prior to the date of the first dose of study drug and continued after the first dose of study drug or any procedure that started on or after the date of the first dose of study drug, but not after the date of the last dose of study drug.

In the situation where an incomplete or missing procedure date is collected, a conservative approach will be taken and it will be counted as a concomitant procedure unless there is evidence that the procedure was performed before the study drug treatment (e.g., an end date before study drug start date). A procedure will be considered a concomitant procedure where one of the following three cases occurs (1) the start date is missing and the end date is either after or on the first study drug dose date; (2) the start date is prior to or on the last dose of study drug and the end date is missing; (3) both the start date and the end date are missing.

Note that a medication or a procedure can be considered both a prior and concomitant medication or procedure if it started prior to the first dose of study drug and continued after the first dose of study drug.

Prior procedures (excluding pancreatic resection), concomitant procedures and study cancer concomitant radiation therapies will be listed by subjects numbers.

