## 5.3 Prohibited Medications and Therapy

---

In addition to the medications listed in the eligibility criteria, use of non-CREON® pancreatic enzyme supplementation or over-the-counter supplements that contain lipase, protease, and amylase as active ingredients, other than the study drug, is prohibited during the treatment period until the last dose of study drug.

Subjects in Screening, who are washing out of PERT, may resume PERT after collecting Stool specimen for Sudan stain test until 1 week prior to Day 1.

**For resected subjects:** Subjects must not have started chemotherapy or radiation therapy from the time of the resection until after Week 1 of the study. However, neoadjuvant therapy prior to the resection is allowed.

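### SAP 7.3 files every incompletely dated medication or procedure as prior without exception, and words the concomitant-medication exception the wrong way round

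*SAP*

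**What the plan says.** SAP 7.3 first gives definitions that assume known dates. A prior medication or procedure is one from before the first dose: "This includes medications and procedures with a start date before the first study drug administration date". A concomitant medication is one begun earlier and continued past the first dose. The definition also has a second limb: "any medication that started on or after the date of the first dose of study drug, but not after the date of the last dose". A closing note lets an item be both prior and concomitant if it began before the first dose and carried on after it.

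The section then sets rules for dates that are incomplete or missing:

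- Prior, for medications and procedures: "a conservative approach will be taken and it will be counted as a prior medication and procedure". No exception follows.
- Concomitant medications: "it will be counted as a concomitant medication unless there is evidence that the medication was not taken before the study drug treatment", with the example "e.g., an end date before study drug start date".
- Concomitant procedures: the same default and the same example, but the exception reads "unless there is evidence that the procedure was performed before the study drug treatment".

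Medications are summarised by generic name. Procedures are listed by subject.

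**The concern.** A partial date often settles the question. If the day is missing but the month and year lie wholly after the first dose, the drug began on study. The prior rule ignores that information. The concomitant exception uses it in the wrong direction, because proof that a drug was not taken before study drug becomes a reason to withdraw the concomitant default.

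At stake is whether the two summaries correctly separate what subjects were taking on entry from what was added during treatment. Protocol 5.4 asks for all chemotherapy used during the study to be recorded. Protocol 5.7 lets a proton pump inhibitor be added only for subjects not already on one. In both cases the reader will want to tell an existing treatment from an added one.

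**Working it through.** The plan states no figure on this point, so the check applies each sentence of SAP 7.3 to constructed records.

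**Inputs.** The first dose is set at 18 January 2021 for illustration. The treatment period is up to 91 days (Protocol synopsis), so Day 91 is 18 January + 90 days = 18 April 2021, taken as the last dose. Medications are recorded through follow-up (Protocol 5.4), and follow-up runs up to 30 days: 18 April + 30 days = 18 May 2021.

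**Records.**

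- A: start March 2021, day missing, ongoing. All of March lies between first and last dose, so it is truly concomitant only.
- B: start January 2021, day missing, ongoing. It is truly concomitant; whether it is also prior cannot be known.
- C: start missing, end 1 October 2020. It is truly prior only.
- D: start May 2021, day missing. It began after the last dose, so it is truly neither.

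**Classification under the text as it stands.**

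| Record | Prior rule | Concomitant: exception as worded | Concomitant: exception read by its example | Concomitant: basic definition |
|---|---|---|---|---|
| A | prior (wrong) | default withdrawn | yes | yes |
| B | prior (acceptable default) | yes | yes | yes |
| C | prior (right) | yes (wrong) | no | no |
| D | prior (wrong) | default withdrawn | yes (wrong) | no |

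**Prior rule.** A and D are filed as prior although the recorded month shows otherwise. This contradicts the definition in the same paragraph. For A it also contradicts the dual-classification note, which covers only items that began before the first dose. The error does not depend on how the concomitant rule is read.

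**Concomitant exception.** Record C is the SAP's own example. On the words it stays concomitant, because nothing shows it was not taken before; on the example it is excluded. Words and example therefore give opposite answers. The procedure sentence, with the same example, agrees with the example, which shows that the medication wording is the slip.

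**Conflict for A.** The exception as worded withdraws the default, while the basic definition makes A concomitant with no imputation. The SAP does not say which prevails, so A may or may not appear in the concomitant summary.

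**Why turning the exception round is not enough.** Read by its example alone, the rule would count D as concomitant. The corrected exception also has to cover a start shown to be after the last dose.

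**The case against.** The best defence is that the intent is plain. The example and the procedure sentence show what was meant, a programmer would probably code to them, and the basic definition captures any drug begun between first and last dose. The SAP calls its approach conservative, meaning inclusive when dates are uncertain. Protocol 5.4 requires date ranges for chemotherapy, and concomitant therapy is reviewed at every visit, so partial dates should be uncommon.

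Much of this stands. A reader might infer that on-study drugs with partial dates are dropped from the concomitant summary. That needs the exception to outrank the basic definition, which the SAP does not say, and a same-month start such as record B is kept on any reading. Any estimate of the share lost would rest on that unstated precedence.

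The defence does not reach the prior rule. Inclusiveness is reasonable where the date leaves doubt, but here the known month removes it. Nor does a clear intent make the wording safe to program from, when the words and the example give opposite results.

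**Conclusion.** The point holds, and it is minor. Under the prior rule, every partial-date record whose known month falls after the first dose is misfiled as prior. Under the concomitant exception, such a record may be kept or left out: anywhere from none to all of those begun on study, depending on which sentence is followed. The documents give no number of partial dates, so no count of affected subjects can be stated. If all dates are complete, nothing changes.

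Three stronger inferences are not supported:

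- **That efficacy or chemotherapy-tolerability results are affected.** The stool fat, stool frequency and EPI symptom models use only treatment and baseline (SAP 9.3.2, 9.4.1, 9.4.2, 9.4.4). Stool consistency uses rank tests (9.4.3), and chemotherapy tolerability uses visit-level questions (9.4.6). No subgroup analysis is planned (9.5). None of these draws on the prior/concomitant class.
- **That misfiled chemotherapy would appear as a breach of Protocol 5.3**, which says "Subjects must not have started chemotherapy or radiation therapy from the time of the resection until after Week 1 of the study". The same section allows neoadjuvant therapy before resection, so an agent in a prior table by generic name shows no breach. Deviations are counted separately (SAP Appendix A).
- **That the procedure rule is wrong to count as concomitant anything begun by the last dose with no end date.** This is inclusive, but defensible for a by-subject listing, and no change is proposed.

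**What to change.** Reword two sentences of SAP 7.3:

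- Prior: a medication or procedure with an incomplete or missing date is counted as prior unless the available part of the start date shows that it started on or after the first dose.
- Concomitant: a medication with an incomplete or missing date is counted as concomitant unless the available part of the dates shows that it ended before the first dose or started after the last dose.

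Applied to the four records, A becomes concomitant only, B stays both, C is prior only and D is neither, which matches the true class wherever it is known. Keeping B in both classes preserves the inclusive default where the date leaves real doubt.

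The cost is SAP wording and a few lines of derivation code. No new data are needed, trial conduct does not change, and no efficacy or safety estimate moves.

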8.0 Handling of Potential Intercurrent Events for the Primary and Key Secondary Endpoints

The primary efficacy endpoint of change in stool fat from Baseline to Week 1 (defined in Section 3.1) will be analyzed based on the EAS-SF and EAS-SF-SUPP population and the following methods will be used to address potential intercurrent events:

• Subjects with missing or incomplete (not evaluable) stool fat sample at either Baseline or Week 1 will be excluded from the analysis.

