## 5.5 Withdrawal of Study Drug and/or Discontinuation of Study

---

A subject may voluntarily withdraw or be withdrawn from study drug administration and/or the study at any time for reasons including, but not limited to, the following:

- The subject requests to be withdrawn from the study.
- The subject becomes pregnant while on study drug.
- The investigator believes it is in the best interest of the subject, for any reason, including:
  - Clinically significant abnormal laboratory results or AEs, which rule out continuation of the study drug, as determined by the investigator.
- Eligibility criteria violation noted after the subject started study drug, if continuation of the study drug administration would place the subject at risk.
- Introduction of prohibited medications or dosages and continuation of the study drug would place the subject at risk.
- Subject is significantly noncompliant with study procedures which would put the subject at risk for continued participation in the trial.

To minimize missing data, subjects who prematurely discontinue study drug treatment should continue to be followed for all regularly scheduled visits. Subjects should be advised on the continued scientific importance of their data even if they discontinue treatment with study drug early.

All attempts must be made to determine the date of the last study drug dose and the primary reason for discontinuation of study drug or study participation. The information will be recorded on the appropriate electronic case report form (eCRF) page. If the subject has not had a study visit 30 days after study drug has been discontinued, a 30-day follow-up phone call after the last dose of study drug will be completed to ensure all treatment-emergent AEs/serious AEs (SAEs) have been resolved.

However, study procedures should not interfere with the initiation of any new treatments or therapeutic modalities that the investigator considers necessary to treat the subject's condition. Following discontinuation of study drug, the subject will be treated in accordance with the investigator's best clinical judgment, irrespective of whether or not the subject decides to continue to participate in the study.

For subjects to be considered lost to follow-up, reasonable attempts must be made to obtain information on the final status of the subject. At a minimum, 2 telephone calls must be made, and 1 certified letter must be sent and documented in the subject's source documentation.

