## 5.7 Randomization/Drug Assignment

---

All subjects will be assigned a unique identification number by the IRT at the Screening Visit. Subjects may rescreen once. For subjects who rescreen, the Screening number assigned by the IRT at the initial Screening visit should continue to be used. For subjects who do not meet the study selection criteria, the site personnel must contact the IRT system and identify the subject as a screen failure.

The IRT will assign a randomization number that will encode the subject's dose cohort assignment according to the randomization schedule generated by the statistics department at AbbVie.

Eligible resected subjects will be randomized to 1 of the 2 dose cohorts in a 1:1 ratio on Day 1 as indicated in Section 4.1.

For resected subjects, all AbbVie personnel with direct oversight of the conduct and management of the trial (with the exception of AbbVie Drug Supply Management Team), the investigator, study site personnel, and the subject will remain blinded to each subject's randomized treatment throughout the study. To maintain the blind, the pancrelipase capsules and placebo capsules provided for the study will be identical in appearance. The IRT will provide access to un-blinded subject treatment information in the case of a medical emergency.

Eligible non-resected subjects will enter the open-label cohort to receive pancrelipase at a dose of 72,000 USP units (Lipase) with meals/36,000 USP units (Lipase) with snacks during the entire duration of the study.

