## 7.2 Definition for Analysis Populations

---

The full analysis set (FAS) includes all randomized subjects who received at least 1 dose of study drug. The FAS will be used for all efficacy and Baseline analyses. Subjects will be grouped according to treatment as randomized. Additional analysis population(s) may be used for the efficacy analysis. Details are provided in the SAP.

The safety analysis set consists of all subjects who received at least 1 dose of study drug. For the safety analysis set, subjects are assigned to a dose cohort based on the treatment actually received, regardless of the treatment randomized.

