### Sample Size Estimation

**Resected subjects:** 72 subjects total (36 subjects per dose group). After adjusting a dropout rate of 16%, the study will have 60 evaluable subjects for the evaluation of stool fat at Week 1. This sample size will have an approximately 99% power to detect a 20 gram stool fat reduction in mean stool fat from Baseline in each dose group assuming that the standard deviation for the change is 25 g or approximately 94% power to detect a 10 g stool fat reduction in mean stool fat from baseline assuming that the SD for the change is 15 g. The type I error rate is 0.05 (2-sided).

In addition, the study will have an approximately 86% power to detect a difference of 20 g between 2 dose groups in mean stool fat change from Baseline, assuming the same standard deviation of 25 g for both dose groups. The power will drop to 63% if the difference is 15 g.

**Non-resected subjects:** Up to 20 subjects.

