9.3.3 Supplementary Analyses of the Primary Efficacy Endpoint(s)

A supplementary analysis will be performed for the primary efficacy endpoint on the subjects included in the EAS-SF-SUPP (subjects with 100% stool sample collected for the 48 hour collection period at both Baseline (Day 1) and Week 1 visits) using the ATG-Day 1 group (High Dose and Low Dose) for the resected population. The change in stool fat from Baseline to Week 1 for each treatment group will be analyzed using the ANCOVA model described in Section 9.3.2.

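### Both stool-fat comparisons use only subjects evaluable at both visits; no stool-fat analysis covers the full analysis set and no table counts the exclusions by arm

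*SAP*

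**What the plan says.** Protocol 7.2 on the efficacy population: "The FAS will be used for all efficacy and Baseline analyses". It groups subjects as randomised, and it adds that further populations may be used, with details left to the SAP.

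For stool fat the SAP does not supplement the FAS; it replaces it. SAP 2.1, 4.0, 9.3.2, 9.4.1 and Table 1 place both the within-cohort primary and the between-dose comparison in EAS-SF (evaluable at both visits) and EAS-SF-SUPP, grouped by the drug dispensed on Day 1. SAP 8.0 gives the exclusion rule: "Subjects with missing or incomplete (not evaluable) stool fat sample at either Baseline or Week 1 will be excluded from the analysis". The supplementary set is narrower still, being limited to "subjects with 100% stool sample collected for the 48 hour collection period at both Baseline (Day 1) and Week 1 visits" (SAP 9.3.3).

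A 24-hour value counts if at least 67% of that day's stools were collected (SAP 9.3.2.1). Missed stools on such a day are allowed for by scaling up, and one evaluable day is enough for a visit. A visit with no evaluable day is left without imputation (SAP 9.2.1).

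On expected loss, the protocol's sample size section says: "After adjusting a dropout rate of 16%, the study will have 60 evaluable subjects for the evaluation of stool fat at Week 1". Protocol 5.5 also asks for follow-up after stopping drug: "To minimize missing data, subjects who prematurely discontinue study drug treatment should continue to be followed for all regularly scheduled visits".

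**The concern.** Membership of EAS-SF depends partly on what happens after randomisation. If subjects without a usable Week 1 sample differ in outcome from those with one, each cohort's mean reduction is off. If that difference is not the same in the two arms, the randomised dose comparison is off as well.

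There are two plausible routes. One is dropout before Week 1. The other is stool frequency, which enters the evaluability rule and is itself a Week 1 endpoint.

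The one supplementary analysis cannot test this. It removes more subjects, so agreement between the two sets says nothing about those excluded from both. The disposition categories in SAP 5.0 do not count non-evaluable samples, so a reader of the report might not learn how many subjects each arm lost, at which visit, or why.

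**Working it through.** **Inputs.** From the protocol's sample size section: 72 randomised, 36 per arm; 16% loss; 60 evaluable; SD of change 25 g or 15 g; two-sided 5% test. The documents do not say how missing and observed subjects differ. That difference, D, is assumed below.

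**1. The plan's own figures reproduce.**
- Evaluable: 72 × 0.84 = 60.5, so about 30 per arm. Expected loss is 72 − 60 = 12, or 6 of 36 per arm (16.7%).
- Within arm, paired t-test, n = 30: SE = 25/√30 = 4.56 g, power for 20 g is 98.8% (stated 99%). SE = 15/√30 = 2.74 g, power for 10 g is 94.2% (stated 94%).
- Between arms, 30 per arm: SE = 25 × √(2/30) = 6.45 g. Power is 86.1% for 20 g and 62.8% for 15 g (stated 86% and 63%).

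**2. What the 67% rule does.** Read literally, one missed stool fails a day with 1 to 3 stools (2/3 = 66.7%) but not a day with 4 or more (3/4 = 75%). Assume each stool is missed independently.

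| Stools per day | Visit evaluable, 10% missed | Visit evaluable, 20% missed |
|---|---|---|
| 2 | 96% | 87% |
| 3 | 93% | 76% |
| 4 | 99.7% | 97% |
| 5 | 99% | 93% |

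Retention therefore depends on frequency, but not in one direction. For EAS-SF-SUPP the direction is clear under the same assumption. With 10% missed, complete two-day collection has probability 0.9² = 81% at 1 stool a day and 0.9⁸ = 43% at 4 a day. With 5% missed the fall is from 90% to 66%; with 20%, from 64% to 17%.

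**3. Within-cohort bias.** Let m be the missing share, R the mean reduction in evaluable subjects, and R − D the mean reduction in missing ones. The mean over all subjects is (1 − m)R + m(R − D) = R − mD, so the evaluable mean overstates by mD.
- D = 10 g: 6/36 × 10 = 1.7 g.
- D = 20 g: 6/36 × 20 = 3.3 g.
- If the true mean change were zero, these biases would raise the nominal 5% within-cohort test to 6.4% and 10.9% (SD 25 g), or 9.1% and 21.7% (SD 15 g).

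**4. Between-dose bias** = m(high) × D(high) − m(low) × D(low).
- Equal loss and equal D: 0 g.
- 6 of 36 lost in each arm, outcome-related in one arm only, D = 20 g: 3.3 g, which is 3.3/6.45 = 0.5 SE. Rejection with no true dose effect is then 8.0%.

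**5. What an FAS check could change.** Suppose the 6 missing high-dose subjects had no advantage over low dose. A 20 g difference becomes 20 × 30/36 = 16.7 g. The smallest significant difference is 12.9 g with 30 per arm and 11.75 g with 36 per arm. An evaluable-set difference between 12.9 g and 11.75 × 36/30 = 14.1 g would therefore lose significance.

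**6. Zero change is not a safe check between doses.** Take an assumed loss of 25% on low dose and 7% on high dose, with both arms' evaluable subjects improving by 15 g. Setting missing change to zero gives 15 × 0.93 − 15 × 0.75 = 2.7 g in favour of high dose, produced by unequal loss alone.

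**The case against.** The strongest reply is that the protocol already points this way. It allows additional populations and sizes the study on 60 evaluable subjects. Its own paired t-test and ANCOVA on change also need both values and specify no imputation, so a protocol FAS analysis run as written would drop every subject without a stool-fat value. That stands. A reader might infer that the SAP breaches the protocol, and the documents do not support that. What remains is that an allowance for additional sets does not explain having no FAS analysis at all. SAP 1.0 refers to Section 12.0 for changes from the protocol, but that section deals only with type I error.

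A reader might also infer that the 67% rule removes subjects with frequent stools, who would be the poor responders. It does not do so by itself, as step 2 shows. That reading needs the further assumption that loose or frequent stools are each missed more often, and nothing in the documents supports it.

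It is also fair that baseline stool is collected on Days −2 and −1, before randomisation, so that loss cannot be caused by the assigned dose. Only Week 1 loss can be, and about a week of treatment leaves limited time for it. Protocol 5.5 asks for continued follow-up after stopping drug.

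Finally, it would be too strong to say that nothing in the plan could reveal a problem. Discontinuations with reasons are reported by randomised dose, and Week 1 stool frequency, consistency and EPI score are compared between doses in the FAS. These are indirect checks. None of them shows what the exclusions do to stool fat.

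The SAP's remark that the study is not for registration is its reason for omitting multiplicity adjustment. It does not bear on this point.

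**Conclusion.** The gap is real but narrower than it may look. Both stool-fat comparisons, including the only randomised one, rest on subjects evaluable at both visits. About one in six subjects is expected to fall outside them, and no planned stool-fat analysis or exclusions table shows whether that matters.

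Bias is possible, not shown, and its direction is not certain. The within-cohort overstatement of 1.7 to 3.3 g rests on 6 of 36 lost and an assumed 10 to 20 g poorer response in those lost. The between-dose bias runs from zero (equal loss, equally related to outcome) to about 3.3 g (one arm's loss outcome-related by 20 g). These amounts are below one standard error at SD 25 g. They would not overturn a clear effect such as the 20 g reduction used for sizing, but they could decide a borderline one.

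Listing missing samples as an intercurrent event, and defining the estimand's population by data availability (SAP Table 2), is a definitional fault that changes no number by itself.

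**What to change.** Keep EAS-SF as the main set, and add to the SAP before unblinding:

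- **One sensitivity analysis of both comparisons** on all resected FAS subjects, grouped as randomised. Impute missing baseline and Week 1 stool fat by multiple imputation within arm, using observed stool fat, stool frequency, stool consistency and EPI score. Then fit the same ANCOVA.
- **A delta-based tipping-point analysis** on the imputed data, with the shift varied separately in each arm.
- **A table of excluded subjects** by arm, visit and reason (no sample, collection below 67%, collection data missing, dropout).
- **Definitions.** State the estimand population as resected FAS subjects, and move missing samples from intercurrent events to missing data.

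Do not present zero change for missing subjects as a conservative analysis of the between-dose comparison.

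The cost is SAP wording and a few extra tables; all the data are already collected. The sensitivity estimates may be less favourable or less precise than the main result.
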